D2. Participants and Recruitment: We will recruit 25 participants in each patient group and 25 healthy Veterans (total N = 75). The groups will be comparable on key demographics (i.e., parental education, gender). Veterans with SCZ will be recruited from the GLA Psychosis Clinic and our MIRECC Patient Registry. Veterans with TBI will be recruited from the Neurobehavior Clinic (directed by [name], co-I on this proposal), and the Polytrauma Clinic at GLA. Selection criteria for all participants include: 1) age 25-55; 2) no other neurological or medical condition interfering with providing informed consent or valid assessment; 3) not meeting diagnostic criteria for current depression *based on the Structured Clinical Interview for DSM-5 (SCID-I)*⁴¹ or depressive symptoms rated moderate or higher (*a rating of 13 or higher on the Hamilton Depression Rating Scale*⁴²); 4) no DSM-V substance use disorder greater than moderate severity in the past 3 months; 5) *no form of cognitive remediation in the 6 months prior to testing*; 6) *an 8th grade reading level assessed with the Wide Range Achievement Test (WRAT)*⁴³; and 7) normal or corrected-to-normal vision and hearing. The age range was chosen to exclude younger participants whose brain development and plasticity is still occurring^{44, 45}, and a conservative upper range where age-related cognitive declines may prominently begin^{46, 47}. *Exclusion criteria for all patient participants include:* 1) *changes in medication dosage or type 3 months prior to testing*; 2) *hospitalization for psychiatric health in the 3 months prior to testing*; 3) *changes in housing status in the 6 months prior to testing*. Full **inclusion/exclusion criteria** and expected ethnicity/race/gender breakdowns are shown in **Human Subjects**.

Clinical Diagnosis: For SCZ, diagnosis will be made with the SCID-I and information from the medical chart. All interviewers are trained through the Treatment Unit of the VA VISN 22 MIRECC to a minimum kappa of 0.75 for key psychotic and mood items, and a minimum intraclass correlation of 0.80⁴⁸. For TBI, participants will have had a concussive or closed-head injury as identified in a structured TBI interview⁴⁹ and meet a mild (*n* =

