D8. Design Considerations: For this SPiRE, we elected to recruit Veteran with any mild or moderate TBI diagnosis from local VA clinics, rather than selecting based on type (e.g., blast vs. impact, closed vs. open) as the sample will be more representative of our VA. We realize the sample may be heterogeneous, with differences in TBI injury, types/doses of medications (e.g., anxiolytics, antidepressants, stimulants), and in comorbid diagnoses (e.g., post-traumatic stress disorder, PTSD). Regarding PTSD, we will assess for presence (meeting DSM-5 criteria) and severity of symptoms (i.e., PCL-5) and examine relationships to the plasticity measures. We will include type of head injury in exploratory analyses. Regarding neuroplasticity assessment, we could have used fMRI or alternative EEG methods. We chose EEG as there are no behavioral measures, and EEG is easier to assess and disseminate in VA clinics than expensive and burdensome fMRI. We chose to assess both STP and LTP as they assess different aspects of neuroplasticity: LTP results in changes at the synapse (e.g., alterations in the number and location of AMPA receptors), whereas STP results in transient changes in synaptic activity not due to structural alterations. Group comparisons are not part of this grant or encouraged by this grant mechanism and we will not formally test for them. However, the data may allow us to see differences in patterns that will suggest differences or similarities in underlying mechanisms and relationships to cognition and community integration in the two patient groups. Given the novel and innovative nature of the research questions, as well as the inclusion of two disorders with similar cognitive deficits, the data from this study will be informative in guiding paradigm development and parameters to be used in a larger Merit. The inclusion of healthy Veterans without cognitive impairments will also be beneficial as these plasticity paradigms have rarely, if ever, been used in these Veterans, and we can apply the same questions of tolerability and feasibility to this group to refine future versions of the tasks to be used in larger grants that will examine group differences.

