D9. Analytic Plan: Consistent with the SPiRE mechanism, statistical analyses will be more descriptive than inferential. For Aim 1 we will assess whether specific targets are met such that at least 90% of those recruited in each group (a) complete the EEG measures and demonstrate tolerability (based on subject self-report *utilizing a questionnaire developed in our lab; see Appendix 1*); and (b) provide high quality EEG data uncontaminated by noise or artifacts and cleaned via traditional methods (e.g., eye-blink correction, artifact rejection). We will also determine the average number of trials needed and the fraction of subjects who fail to achieve within-session reliability (cutoff of 0.8 for internal consistency), allowing us to optimize the paradigms for future studies. For Aim 2, we will examine the distributional properties of the neuroplasticity measures in each group to ensure that they show sufficient variability to be useful as potential biomarkers, provide estimates of key parameters (e.g., mean, SD), and inform the need for transformations or other specialized analytic approaches. For Exploratory Aim 3 we will use correlational analyses to assess the relationships of neuroplasticity measures with downstream cognitive and functional outcomes as well as demographic and clinical characteristics, *as well as the relationships between the two neuroplasticity measures themselves*.

References

1. Green, M.F., G. Hellemann, W.P. Horan, et al., *From perception to functional outcome in schizophrenia: modeling the role of ability and motivation*. Archives of General Psychiatry, 2012. **69**(12): p. 1216-24.
2. Sander, A.M., A. Clark, and M.R. Pappadis, *What is community integration anyway?: defining meaning following traumatic brain injury*. J Head Trauma Rehabil, 2010. **25**(2): p. 121-7.
3. Baser, O., L. Xie, J. Pesa, et al., *Healthcare utilization and costs of veterans health administration patients with schizophrenia treated with paliperidone palmitate long-acting injection or oral atypical antipsychotics*. Journal of Medical Economics, 2015. **18**: p. 357-365.
4. Taylor, B.C., E. Hagel Campbell, S. Nugent, et al., *Three Year Trends in Veterans Health Administration Utilization and Costs after Traumatic Brain Injury Screening among Veterans with Mild Traumatic Brain Injury*. J Neurotrauma, 2017. **34**(17): p. 2567-2574.

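### Does Aim 1 need a planned confidence interval around its 90% feasibility target in groups of 25?

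*Combined protocol and SAP*

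**What the plan says.** Section D9 (Analytic Plan) opens by stating that "statistical analyses will be more descriptive than inferential". For Aim 1 it will "assess whether specific targets are met such that at least 90% of those recruited in each group" satisfy two conditions: (a) they "complete the EEG measures and demonstrate tolerability", with tolerability taken from a self-report questionnaire, and (b) they "provide high quality EEG data uncontaminated by noise or artifacts and cleaned via traditional methods". In the same aim it will "determine the average number of trials needed and the fraction of subjects who fail to achieve within-session reliability", using a cutoff of 0.8. Section D2 sets 25 participants for each of the three groups, 75 in all.

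Section D8 describes the use of the results. The study's data are to be "informative in guiding paradigm development and parameters to be used in a larger Merit", and for healthy Veterans the investigators write that "we can apply the same questions of tolerability and feasibility to this group to refine future versions of the tasks".

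The supplied text gives no confidence interval for the Aim 1 proportions, no reason for choosing 25 against the 90% target, and no rule for reading a near miss. Appendix 1 and the Human Subjects section are cited but are not in the supplied text.

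**The concern.** A fixed cut on an observed proportion looks like a decision rule, and 25 people cannot locate a rate near 90% closely. One participant moves a group from 88% (missed) to 92% (met), although the two results carry nearly the same information about the underlying rate. If all three groups truly sat at 90%, it would be likely that at least one missed by chance.

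Because D8 says the study will shape the tasks for a larger grant, a verdict read without its precision could mislead in either direction. A chance miss could prompt needless redesign, and a chance pass could carry a weak paradigm forward.

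**Working it through.** **Inputs.** Group size 25 (D2) and target 90% of those recruited, per group (D9). The documents state no alpha, power or confidence level, so there is no statistical figure of the plan's own to reproduce. The two-sided 95% level below is an assumption.

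**Count behind the target.** 0.90 × 25 = 22.5, so the smallest count that meets it is 23. 22/25 = 88% and 23/25 = 92%.

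**Chance that one group meets one target.** With X binomial (25, p), P(X ≥ 23) = 300·p²³(1−p)² + 25·p²⁴(1−p) + p²⁵. At p = 0.90 this is 0.2659 + 0.1994 + 0.0718 = 0.537.

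| True rate | P(target met) | P(target missed) |
|---|---|---|
| 75% | 3.2% | 96.8% |
| 80% | 9.8% | 90.2% |
| 85% | 25.4% | 74.6% |
| 90% | 53.7% | 46.3% |
| 95% | 87.3% | 12.7% |
| 98% | 98.7% | 1.3% |

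The rule discriminates poorly between about 85% and 95%, and well outside that range. A miss rate near one half at a true 90% is what any cut placed at the true value produces.

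**Three groups, one target.** Assuming independent groups with a common true rate of 90%, P(at least one misses) = 1 − 0.5371³ = 84.5%. At 95% it is 1 − 0.8729³ = 33.5%.

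**Exact (Clopper-Pearson) 95% intervals.**

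| Count | Observed | Interval |
|---|---|---|
| 18/25 | 72% | 50.6% to 87.9% |
| 19/25 | 76% | 54.9% to 90.6% |
| 22/25 | 88% | 68.8% to 97.5% |
| 23/25 | 92% | 74.0% to 99.0% |
| 25/25 | 100% | 86.3% to 100% |

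Every count from 19 to 25 has an interval that includes 90%. Even a perfect score does not put the lower limit above 90%.

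**Would pre-set reading bands help?** One could label 23 to 25 as met, 19 to 22 as inconclusive and 18 or fewer as below target. The line between the first two bands is the existing 90% target again. The labels also depend on exactly 25 being recruited, whereas D9's denominator is the number actually recruited. At 24 recruited, 18/24 has an upper limit of 90.2%, so it would no longer lie below 90%. At 26 recruited, 23/26 = 88.5%, which misses the target.

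**The case for a change.** The strongest case for a change is that an interval is itself a descriptive summary, so calling the analysis descriptive does not excuse leaving it out. D9 commits only to assessing whether targets are met, while for Aim 2 it promises parameter estimates, and the natural parameters of Aim 1 are these proportions. A reading of near misses stated in advance also cannot be supplied afterwards by a reader. The remedy costs only wording.

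Part of this stands. The supplied text mentions no interval, the arithmetic is right, and an interval beside each proportion would be good reporting practice.

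The rest does not carry. Judging a 90% target requires a count and a denominator, and nothing in D9 says they will be withheld; anyone given 23/25 can compute the interval. The 84.5% figure describes an all-groups success rule that the plan does not contain. The link to later decisions is also looser than it looks. In D8 it is the study's data as a whole that inform the larger grant. In D9 the remark about optimizing the paradigms follows the trial counts and the reliability fraction, not the 90% targets. Only the healthy-Veteran sentence in D8 ties tolerability and feasibility directly to task refinement, and it sets no threshold for doing so.

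**Conclusion.** No change is called for. The plan is silent on the precision of two feasibility proportions, a gap that a competent analyst fills when reporting. Followed as written, D9 gives a sound descriptive answer: whether the observed share in each group reached 90%. Adding intervals would leave the target and every met or missed label as they are. No test, error rate, go/no-go decision or claim about a true rate rests on the target.

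The imprecision near the target is substantial: a 46.3% chance of missing at a true 90%, a 25.4% chance of passing at a true 85%, and 95% intervals about 25 to 29 percentage points wide at 23/25 and 22/25 (99.0 − 74.0 = 25.0; 97.5 − 68.8 = 28.7). That comes from having 25 per group, and wording cannot reduce it. For a pilot meant to tell workable tasks from unworkable ones, the rule does its job, with 3.2% passing at a true 75% and 98.7% at a true 98%.

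Whoever reports Aim 1 may reasonably give the count, the proportion of those actually recruited and an exact interval for each group and target, and should not present a met target as proof of a true rate of at least 90%. This conclusion rests on the supplied text, on independent participants for the binomial figures, and on the assumed 95% level.

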Neuroplasticity in TBI and Schizophrenia

Principal Investigator: [name].

NCT03995368

February 26, 2024

A. Research Plan

Veterans with cognitive deficits represent a substantial service and financial burden at the Veterans Administration (VA). Importantly, even with treatment, these Veterans have severe problems with community integration^{1, 2}, defined as the ability to return to full participation in major life roles including competitive employment, school, and supportive social/family networks. Two prominent patient groups within the VA with cognitive deficits and poor community integration are schizophrenia (SCZ) and traumatic brain injury (TBI). SCZ and TBI are common, devastating conditions among Veterans and require high levels of VA healthcare and disability resources. The average annual treatment cost is \$31,000/patient with SCZ³ and three times as high for Veterans with TBI compared to those without⁴. While SCZ and TBI differ in terms of etiology and clinical presentation (SCZ is considered a neurodevelopmental disorder⁵ while TBI is acquired), the determinants of poor community integration are overlapping in the two disorders: *both share features of social⁶ and non-social cognitive deficits^{7, 8}, which are both highly related to poor community integration⁹⁻¹¹. Most of the research on connections to community integration has been done in SCZ and the associations are generally stronger for social cognition than non-social cognition¹².* Evidence indicates that neuroplasticity impairments underlie cognitive deficits in both SCZ and TBI. This SPiRE aims to examine neuroplasticity in these two disorders using novel neurophysiological measures and to evaluate the statistical properties of those measures in each patient population, a necessary step for determining whether they are suitable for assessing individual differences and to serve as biomarkers in future treatment studies.

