A1. Neuroplasticity: Neuroplasticity is defined as the malleability of neural organization in response to both endogenous experiences (e.g., cognitive functioning, emotions) and exogenous experiences (e.g., neurostimulation using electricity or magnetic pulses, pharmacological agents). Neuroplasticity is typically studied on two different time frames: short term potentiation (STP), which is the transient facilitation or depression of synaptic activity posited to underlie processes such as sensory adaptation on the order of seconds^{13, 14}, and long-term potentiation (LTP), which is an enduring structural change of the synapse lasting hours to months. Neuroplasticity is posited to be the neural basis of learning and memory¹⁵.

A2. The relevance of neuroplasticity to SCZ and TBI: There is strong evidence that both SCZ and TBI are associated with impaired neuroplasticity^{16, 17}. Dysfunctional neuroplasticity is implicated in SCZ patients' cognitive deficits¹⁸. Animal models demonstrate that impairments in neuroplasticity are present after injury in TBI¹⁷. Neuroplasticity, including both STP and LTP, is thought to be mediated by *N*-methyl-D-aspartate (NMDA) receptors. One of the leading neurochemical hypotheses of schizophrenia is that it involves NMDA receptor dysfunction¹⁹, with NMDA antagonists (e.g., ketamine) inducing schizophrenia-like symptoms in healthy individuals²⁰. In TBI, alterations of the NMDA receptor after trauma are thought to lead to excitotoxic damage²¹ and subsequently impaired neuroplasticity. These findings implicate NMDA-mediated neuroplasticity in both SCZ and TBI. While the NMDA system may be involved in both disorders, we do not know if the same or different mechanisms contribute to dysfunctional neuroplasticity. New treatments that target the root causes of cognitive deficits in SCZ and TBI would be highly valuable for VA's efforts to promote interventions in these Veteran populations. Correspondingly, it is critical to develop objective outcome measures to evaluate the efficacy of such interventions. The current proposal addresses this critical treatment development prerequisite by building on our work with non-invasive EEG paradigms designed to assess neuroplasticity *in vivo*.

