We view this proposal as a necessary first step that will provide innovative insights into neuroplasticity in Veterans with neurodevelopmental or acquired cognitive disorders and will help inform treatment development in future studies. Examining EEG-based measures of neuroplasticity is a small but growing area of research that has not yet been extended to Veterans, except for work by our own lab in Veterans with schizophrenia. Regarding innovation, this would be the first study to examine *in vivo* neuroplasticity measures (both STP and LTP) in Veterans with TBI. Regarding treatment implications, we can use the assessment tools derived from this study to test the effectiveness of plasticity-based interventions, including specialized cognitive remediation or neurostimulation approaches, on improving cognition and community integration in Veterans with cognitive disorders. *It is also possible to use the ERPs to predict treatment response; for example, MMN has been shown to predict treatment response to cognitive remediation in SCZ³⁷.* Our VA Research Enhancement Award Program (REAP) on Community Integration in Homeless Veterans ([name], PI) has shown that SCZ and TBI are major risk factors for homelessness and barriers to community reintegration among Veterans. A novel future direction could extend our assessments of and treatments for neuroplasticity to homeless Veterans. Finally, we could examine physiological factors that influence plasticity biomarkers derived from this study. For example, evidence shows that abnormal neuroinflammation, seen in both SCZ³⁸ and TBI³⁹, impairs plasticity and cognition in animals³⁸. Examining how neuroinflammation and neuroplasticity interact in Veterans with these disorders would be highly informative and point to anti-inflammatory treatments to improve plasticity and cognition.

C. Preliminary Studies

A focus of our lab has been to examine determinants of functional outcome and community integration in Veterans with SCZ and other serious mental illnesses using self-report, clinical interviews, behavior, EEG, and neuroimaging. Our work in SCZ demonstrates that the PI and research team are qualified to conduct the proposed research in

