	Table 1: Timeline of Activities (per quarter of project)							
	Year 1				Year 2			
	Q1	Q2	Q3	Q4	Q1	Q2	Q3	Q4
Startup								
Recruitment and Data Collection (n = 12-13 per quarter)								
Analysis, Write-Up, MERIT Application								

biomarkers of STP and LTP in Veterans with (either SCZ or TBI) or without (healthy Veterans) cognitive disorders. This study will leverage three aspects of existing research infrastructure at the GLA: 1) the VISN 22 MIRECC (laboratory assessment space, interviewer training); 2) the MIRECC Data Core (statistical and data management/quality assurance support); and 3) the REAP (Director: [name].). These are fully described in the **Resources** section. Institutional Review Board (IRB) and start-up activities, including creating a secure on-line data entry and storage system with the Data Core, will be accomplished in the first quarter of the study. Recruitment will continue up through Q3, Year 2. Q4 of Year 2 will focus on data analysis, dissemination through scientific presentations and publications, and preparation of a MERIT application.

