D4. Clinical interviews and scales: A comprehensive psychiatric and social history form developed by our lab will be used to record additional information that may be of interest to consider in secondary analyses, such as duration of illness, socioeconomic status, and cigarette smoking status. We will administer the SCID⁴⁴ to all potential participants, and the SCID-Personality Disorders⁵³ to healthy Veterans only. Clinical symptoms for all participants will be assessed with the Expanded Brief Psychiatric Rating Scale⁵⁴, the Clinical Assessment Interview for Negative Symptoms⁵⁵, the Hamilton Depression Rating Scale⁴², the Patient Health Questionnaire⁵⁶, the Young Mania Rating Scale⁵⁷, PTSD Checklist (PCL-5)⁵⁸, and the Addiction Severity Index⁵⁹. These measures will be used to characterize the samples and explore relationships to plasticity.

D5. ERP Recording and Analysis Procedures: ERP recording and processing will use existing equipment in the lab of [name] at the VISN22 MIRECC (see Facilities and Other Resources). Stimulus presentation and EEG data synchronization will use Presentation (Neurobehavioral Systems, Inc, Berkeley, CA). EEG will be collected continuously using a 64-channel BioSemi ActiveTwo amplifier (BioSemi, Germany), sampled at 512 Hz from DC to 100 Hz. Four electrodes to monitor horizontal and vertical electrooculogram will be used to correct for eye blinks and other movements using established methods⁶⁰. Data will be processed with Brain Vision Analyzer 2, EEGLab⁶¹, Mass Univariate Analysis Toolbox⁶², and PCA Toolbox⁶³ using established methods to obtain and analyze ERPs (e.g.,⁶⁴⁻⁶⁶).

Evaluation of Within-Session Reliability (Internal Consistency): In order to validly use ERPs to make inferences, ERP components must demonstrate acceptable reliability^{67, 68}. ERP score reliability provides an estimate of signal-to-noise ratio (SNR). Ensuring adequate reliability is critical when comparing ERP scores from different task conditions, because condition differences can be obscured by low SNR. Similarly, low score reliability imposes an upper limit on correlations with other variables, such as cognitive scores. Hence, poor score reliability can limit effect sizes for both between-condition differences and correlations with other variables. We will use the ERP Reliability Analysis (ERA) Toolbox, which utilizes G

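### Aim 2 judges the plasticity scores by observed spread, but the planned reliability check is not stated for those difference scores, so measurement error can count as useful variability

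*Combined protocol and SAP*

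**What the plan says.** **Purpose.** Section A presents the study as a step towards "determining whether they are suitable for assessing individual differences and to serve as biomarkers in future treatment studies". Section B adds that "we can use the assessment tools derived from this study to test the effectiveness of plasticity-based interventions", although that section opens by describing the proposal as a first step.

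**Aim 2.** D9 describes the analyses as mainly descriptive. Under Aim 2 the distributions are examined "to ensure that they show sufficient variability to be useful as potential biomarkers", to estimate quantities such as the mean and SD, and to see whether transformations are needed. D9 gives no threshold for sufficient variability, and reliability is not mentioned under this aim.

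**Reliability.** Under Aim 1, D9 will report "the fraction of subjects who fail to achieve within-session reliability (cutoff of 0.8 for internal consistency". It does not name the score to which the cutoff applies. D5 attaches the 0.8 standard to an ERP and describes the toolbox output by condition and group.

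**Plasticity scores.** In D5 the short-term score is the MMN after 36 standards minus the MMN after 2, and each MMN is itself deviant minus standard. The long-term effect is the VEP after modulation compared with the VEP before it. There are 80 stimuli of each type before modulation and 40 of each type in each of three later blocks.

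**Repeat measurement.** The roving MMN task runs between the post-modulation blocks, and the only repeats are at 5, 15 and 25 minutes. D1, D5 and D9 describe no second EEG day and no retest analysis.

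**The concern.** The variance of a score across people is the sum of stable differences between them, their state on the day, and measurement error. A criterion based on spread alone treats all three as useful. A score made only of error has spread too, and so would meet it.

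D5 already recognises that low reliability hides condition differences and caps correlations with cognition. That reasoning is not carried into Aim 2, where usefulness is judged, or stated for the scores that Aim 2 judges. Subtracting one condition from another removes the variance they share but keeps the error of both, so a difference is usually less reliable than its parts.

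At stake is what the later Merit application takes from this study. An SD that is largely error could be read as evidence that Veterans differ in plasticity. The weak correlations expected from such a score in Exploratory Aim 3 could be read as a lack of relationship.

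**Working it through.** **1. The plan's own figure.** D2 sets three groups of 25: 3 x 25 = 75, as stated. Table 1 gives 12 to 13 people per quarter. Recruitment from Year 1 Q2 to Year 2 Q3 is 6 quarters, so 6 x 12 = 72 to 6 x 13 = 78, which agrees. No precision, power or reliability calculation is given for the plasticity scores.

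**2. Reliability of a difference.** Take two condition scores with equal observed variance V, reliability R each, observed correlation r, and uncorrelated errors.
- Observed variance of the difference: 2V(1 - r).
- Error-free variance of the difference: 2V(R - r).
- Reliability of the difference: (R - r)/(1 - r).

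R = 0.8 is the plan's cutoff. The documents give no value of r, so it is an assumption.

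| r | Reliability of difference | Error share of variance | Raw SD / error-corrected SD |
|---|---|---|---|
| 0 | 0.8/1.0 = 0.80 | 20% | 1/√0.80 = 1.12 |
| 0.4 | 0.4/0.6 = 0.67 | 33% | 1/√0.67 = 1.22 |
| 0.5 | 0.3/0.5 = 0.60 | 40% | 1/√0.60 = 1.29 |
| 0.6 | 0.2/0.4 = 0.50 | 50% | 1/√0.50 = 1.41 |
| 0.7 | 0.1/0.3 = 0.33 | 67% | 1/√0.33 = 1.73 |
| 0.8 | 0/0.2 = 0 | 100% | not defined |

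Both conditions meet the cutoff in every row. The difference meets it only at r = 0. At r = 0.5 the conditions would need R = 0.9 for the difference to reach 0.8: (0.9 - 0.5)/(1 - 0.5) = 0.80.

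If the two reliabilities differ, as the 80 and 40 VEP stimuli make likely, R is replaced by their average as long as the variances remain equal.

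**3. Effect on Aim 3.** The largest correlation such a score can show with a perfectly measured variable is the square root of its reliability: √0.60 = 0.77, √0.50 = 0.71, √0.33 = 0.58.

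**4. What spread and reliability can each detect.** A simulation of 25 people, repeated 20,000 times with assumed variance shares that sum to 1, gives these medians:

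| Make-up of the score | SD | Within-session reliability | Correlation with a second day |
|---|---|---|---|
| Stable 0.8, error 0.2 | 0.99 | 0.81 | 0.81 |
| Stable 0.4, state 0.4, error 0.2 | 0.99 | 0.81 | 0.41 |
| State 0.8, error 0.2 | 0.98 | 0.81 | 0.00 |
| Error only | 0.99 | 0.00 | 0.00 |

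The SD does not separate any of the four. Within-session reliability computed on the score itself exposes the last row. It cannot separate the first three, because that requires a second day.

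**The case against.** **The Aim 1 check already covers noise.** This is the strongest reply, and it stands in part. If the 0.8 cutoff is applied to the plasticity scores, a mostly noisy score will be flagged. D9 does not rule that out, but neither D5 nor D9 says it. Even then, the result is reported under Aim 1 and does not condition the Aim 2 judgement.

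**The plan claims little.** This also stands. The work is called a first step, the measures are potential biomarkers, and the analyses are mainly descriptive. A reader might infer from section B that one session will clear the measures as pre-post endpoints, or that the pilot is deficient without a retest visit. The documents do not support either reading: they never say that one session is enough, and a descriptive pilot needs no retest if its conclusions are worded to match.

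**Aim 2 does not select scores.** A reader might infer that Aim 2 would choose the noisier of two candidates. It has no rule that ranks scores by SD. The short-term score is fixed in advance, and the VEP components come from the post-pre contrast and the PCA.

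**Carry-over is not shown.** Section A1 describes LTP as a process "which is an enduring structural change of the synapse lasting hours to months", so a reader might infer that a second modulation would start from an altered baseline. A1 is defining synaptic LTP in general. For the visual EEG methods, A3 reports an effect of up to an hour, so the documents give no ground for expecting carry-over to another day.

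**A single session is inferred.** No sentence states it, and the Human Subjects section is not in the available text. The sections on design, EEG and analysis describe no repeat visit.

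**Conclusion.** The point holds as a gap in the Aim 2 criterion and a limit on its conclusion. It is not an error in a stated number. Both conditions can meet the 0.8 cutoff while the difference between them has reliability 0.60, 0.50 or 0.33, so that the raw SD exceeds the error-corrected SD by a factor of 1.29, 1.41 or 1.73. These figures assume equal variances, uncorrelated errors, condition scores exactly at the cutoff, and correlations of 0.5 to 0.7. If the conditions correlate weakly or are more reliable than 0.8, the loss is smaller.

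For state on the day, no planned analysis can help, since the design as described has no second day. That calls for a narrower conclusion and does not call for a new visit.

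**What to change.** In D9:

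1. Compute within-session reliability on each plasticity difference score itself, in each group: MMN after 36 minus after 2 standards, and post minus pre modulation for each VEP component and time point analysed.
2. Make the existing 0.8 standard on that score part of the Aim 2 judgement of sufficient variability.
3. Report the error-corrected between-person SD (observed SD x square root of that reliability) beside the raw SD. The raw SD remains the figure for planning a later study that uses the observed score.
4. Limit the Aim 2 conclusion to single-session individual differences, and state that between-day stability is not assessed. Align the related statements in sections A and B.

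The second step is needed because a corrected SD alone can still favour a noisy score. With illustrative values, an SD of 3.0 uV at reliability 0.3 gives 3.0 x √0.3 = 1.64, while an SD of 1.5 uV at reliability 0.8 gives 1.5 x √0.8 = 1.34.

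The cost is a small amount of analysis that the text does not now describe, run on data already to be collected. Corrected SDs will be smaller than raw SDs, some plasticity scores may miss 0.8 although their components reach it, and the claim becomes narrower. No extra visit or participant is needed.
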